1 SUMMARY

PD0049 is a pilot study to investigate whether motor symptoms in subjects with Parkinson's disease who start treatment with Neupro[®] can be improved by using wearable devices. Specifically, this study focuses on investigating how to optimize the evaluation of motor symptoms in subjects with Parkinson's disease aiming at enabling Investigators to optimize subjects' Neupro dosing regimens and ensure better patient outcomes in a timelier manner.

In this study, 2 Kinesia devices (Kinesia-ONE and Kinesia-360) will be employed to record specific motor symptoms. Approximately 40 subjects with Parkinson's disease of any stage will be randomized (1:1 ratio) to either the Control Group or the Experimental Group. Specific motor tasks will be measured in all subjects with Kinesia-ONE on Day 1. In contrast to subjects randomized to the Control Group, subjects randomized to the Experimental Group will also use the Kinesia-360 device for home-based self-recording of their motor symptoms.

All subjects will start Neupro treatment at a dose of either rotigotine 2mg/24h or 4mg/24h (according to the disease stage of the subject), which will then be adjusted based on symptom assessment either via standard care alone (Control Group) or via a combination of standard care and evaluation of the recordings made available by the Kinesia wearable technologies (Experimental Group). The Neupro dosing regimen used in PD0049 follows standard of care, and is in line with the approved dosing regimen for rotigotine in the treatment of Parkinson's disease (ie, up to 8mg/24h, depending on the stage of the disease).

PD0049 starts with in-clinic Screening activities, assessments (including recording of Baseline motor symptoms via Kinesia-One), and training in the use of Kinesia-360 devices (for subjects randomized to the Experimental Group only) on Day 1, followed by 3 days at home: During this period, subjects randomized to the Experimental Group will use the Kinesia-360 device to record their motor symptoms (on Days 2 and 3). Subjects allocated to the Control Group will start treatment with Neupro preferably on Day 1 (but no later than Day 4); subjects allocated to the Experimental group will start treatment with Neupro on Day 4. There are no required visits from Week 2 up to Week 12 (Visit 2). However, Investigators and subjects in the Experimental Group are encouraged to discuss by phone Kinesia-360 motor symptom reports and needs for any changes in Neupro dosing. Subjects of either group return to the clinic for final assessments and reporting of adverse events (AEs) and concomitant medications at Week 12. The individual duration of study participation may last up to 12 weeks.

A primary objective of PD0049 is to evaluate whether Parkinson's disease motor symptoms in subjects starting Neupro can be improved by using feedback of motor symptom data from the Kinesia-360 wearable technology presented to subjects and Investigators in addition to standard clinical practice as compared with only standard clinical practice. A primary objective is to evaluate whether a clinician is more likely to determine a Neupro dosing regimen that improves a subject's Parkinson's disease motor symptoms when using motor symptom data collected with the Kinesia-360 wearable technology in addition to standard clinical practice as compared with only standard clinical practice. Another primary objective is to evaluate whether subjects with Parkinson's disease are more likely to continue the usage of Neupro if Parkinson's disease motor symptom data collected using the Kinesia wearable technology is used to provide the subjects with feedback on the status of their Parkinson's disease motor symptoms and is used in addition to standard of care for titrating their Neupro dosing regimen. Other objectives include to evaluate

the quality of life and engagement in the management and treatment of their disease within subjects in either group, as well as to evaluate the safety of Neupro. The corresponding variables to be assessed to meet the study objectives are described in detail in [Section 4](#).

2 INTRODUCTION

Neupro is approved for the treatment of the signs and symptoms of early-stage idiopathic Parkinson's disease as monotherapy (ie, without levodopa) or in combination with levodopa, ie, over the course of the disease, through to late stages when the effect of levodopa wears off or becomes inconsistent and fluctuations of the therapeutic effect occur (end of dose or "on-off" fluctuations).

Dosing in patients with early-stage Parkinson's disease consists of a single daily dose initiated at rotigotine 2mg/24h and then increased in weekly increments of rotigotine 2mg/24h to an effective dose up to a maximum dose of rotigotine 6mg/24h. Rotigotine 4mg/24h may be an effective dose in some patients. For most patients an effective dose is reached within 3 or 4 weeks at doses of rotigotine 6mg/24h. The maximum approved dose is rotigotine 6mg/24h (NEUPRO [package insert]. 2016 [[Section 15](#)]).

Dosing in patients with advanced-stage Parkinson's disease with fluctuations consists of a single daily dose that should be initiated at rotigotine 4mg/24h and then increased in weekly increments of rotigotine 2mg/24h to an effective dose up to a maximum dose of rotigotine 8mg/24h. Rotigotine 4mg/24h or rotigotine 6mg/24h may be effective doses in some patients. For most patients with advanced-stage Parkinson's disease, an effective dose is reached within 3 to 7 weeks at doses of rotigotine 8mg/24h. The maximum approved dose is rotigotine 8mg/24h (NEUPRO [package insert]. 2016 [[Section 15](#)]).

Optimal patient outcomes may be expected only when the clinician is able to prescribe a customized, optimal dosing regimen for patients with Parkinson's disease. Clinicians employ various measures to diagnose Parkinson's disease and its severity in order to prescribe the optimal dosing regimen for the patient. Key amongst these measures is an evaluation of the severity of the motor symptoms (eg, dyskinesia, gait, tremor, rigidity, and posture) associated with Parkinson's disease. The quality of this evaluation (ie, quantification of movement) is critical to an accurate diagnosis of the evaluation of severity of the motor symptoms and is currently limited by the ability of the Clinician (through manual manipulation and observation) to accurately measure the various physical manifestations of motor symptoms associated with Parkinson's disease. Ultimately, the quality of the evaluation of the motor symptoms may determine whether the Clinician is able to prescribe the optimal dosing regimen for the patient.

New, wearable technologies that allow for accurate, consistent, and ongoing measurement of motor activity under ambulatory conditions in patients with Parkinson's disease may provide the Clinician with additional motor symptom data that the Clinician could use to make more accurate evaluations of the motor symptoms associated with Parkinson's disease, thereby providing the patient with the optimal Neupro dosing regimen and ensuring better patient outcomes in a more timely manner.

The focus of this 12-week study is on optimizing patients' response to Neupro by using a commercially available wearable device to optimize the evaluation of motor symptoms and to improve customized dosing.

3 STUDY OBJECTIVES

3.1 Primary objectives

The primary objectives of this study are to:

- Evaluate whether Parkinson's disease motor symptoms in subjects starting Neupro can be improved by using feedback of motor symptom data from the Kinesia-360 wearable technology presented to subjects and Investigators in addition to standard clinical practice as compared with only standard clinical practice.
- Evaluate the Neupro dosing regimen when using feedback of motor symptom data collected with the Kinesia-360 wearable technology in addition to standard clinical practice as compared with only standard clinical practice.
- Evaluate whether subjects with Parkinson's disease are more likely to continue the usage of Neupro if Parkinson's disease motor symptom data collected using the Kinesia-360 wearable technology is used to provide the subjects with feedback on the status of their Parkinson's disease motor symptoms and is used in addition to standard of care for titrating their Neupro dosing regimen.

3.2 Other objectives

Other objectives of this study are to:

- Evaluate whether the quality of life of subjects with Parkinson's disease can be improved by using the Kinesia-360 wearable technology to collect motor symptom data in addition to standard clinical practice as compared with only standard clinical practice to titrate the Neupro dosing regimen.
- Evaluate whether subjects with Parkinson's disease are more actively engaged in the management and treatment of their disease with Neupro therapy with the use of the Kinesia-360 wearable technology as compared to without the use of the Kinesia-360 wearable technology.
- Evaluate the safety of Neupro.

4 STUDY VARIABLES

4.1 Efficacy variables

4.1.1 Primary efficacy variables

The efficacy variables of this study are:

- Change from Baseline (Visit 1/Week 1) to Visit 2 (Week 12/3 months after start of treatment with Neupro) in Unified Parkinson's Disease Rating Scale (UPDRS) Part III Motor Score.
- Change from Baseline (Visit 1/Week 1) to Visit 2 (Week 12) in Kinesia-ONE variables:
 - finger tapping speed score
 - rest tremor score
 - averaged finger tapping speed and resting tremor scores
 - postural tremor score
 - finger tapping amplitude score
 - hand grasp speed score
 - hand grasp amplitude score
 - rapid alternating movement speed score
 - rapid alternating amplitude score
 - dyskinesia score
- Neupro dose per 24h at Visit 2 (Week 12)
- Number of Neupro dose changes during the study (between Visit 1 and Visit 2)
- Discontinuation of treatment with Neupro during the course of the study

4.1.2 Other efficacy variables

- Change from Baseline to Visit 2 in the motor scores derived from the Kinesia-360 wearable technology by time (weekly/monthly) and by Neupro dose level (mg/24h) for the Experimental Group in:
 - average daily tremor score
 - average daily slowness score
 - average daily dyskinesia score
 - percent wear-time tremor detected
 - percent wear-time dyskinesia detected
 - percent wear-time user not moving
 - percent wear-time user was walking score
 - percent wear-time user active but not walking

- number of steps per hour while wearing device
- Change from Baseline to Visit 2 (Week 12) in the 39-Item Parkinson's Disease Questionnaire (PDQ-39) scores.
- Change from Baseline to Visit 2 (Week 12) in subject engagement questionnaire scores.

4.2 Safety variables

Safety variable is:

- Occurrence of AEs

5 STUDY DESIGN

5.1 Study description

PD0049 is a multicenter, open-label, two-arm, 12-week study in subjects with Parkinson's disease. On Day 1, eligible subjects will be randomized to either the Control Group or the Experimental Group in a 1:1 fashion. In both groups, subjects will use the Kinesia-ONE wearable device in-clinic at Visit 1 and Visit 2 for recording of specific motor symptoms, and subjects randomized to the Experimental Group will also use the Kinesia-360 wearable device at home while awake for continuous measurement of motor symptoms. The Investigator will use these symptom data to provide feedback to subjects on their motor symptoms and to supplement standard of care to titrate the optimal dose of Neupro for any given subject. In the Control Group, subjects will not use any wearable device at home, and the Investigator will use only standard of care to titrate the optimal Neupro dose.

Subjects in the Control Group and the Experimental Group will start treatment with Neupro 2mg/24h or 4mg/24h (at the Investigator's discretion and according to the disease stage of the subject) preferably on Day 1 (but no later than Day 4) or Day 4, respectively. Evaluations conclude 12 weeks after the start of treatment with Neupro (ie, at Visit 2).

The decision to prescribe Neupro must be made by the Investigator independent of his/her decision to include the subject in the study. The subject's treatment/Neupro intake must be within the terms of the marketing authorization; Neupro will not be supplied by UCB.

A schedule of study assessments is presented in [Table 5-1](#); for a detailed rationale of the study design see [Section 5.3](#).

5.1.1 Study duration per subject

Each subject's participation is approximately 12 weeks.

The end of the study is defined as the date of the last visit of the last subject in the study.

5.1.2 Planned number of subjects and sites

This study will be conducted in approximately 6 sites and will include a total of approximately 40 subjects (20 subjects in the Experimental Group and 20 subjects in the Control Group). Of note, a single site will not randomize more than 20 subjects.

5.1.3 Anticipated regions and countries

This study will be conducted in the US.

5.2 Schedule of study assessments

A schedule of assessments planned for both the Control Group and the Experimental group is presented in [Table 5-1](#).

This document cannot be used to support any marketing authorization application and any extensions or variations thereof.

REDACTED COPY

Table 5–1: Schedule of study assessments

Assessments	In Clinic		At Home					In Clinic
	SCREENING	BASELINE						EOS/EW
	Visit 1						Visit 2	
	Day 1	Day 2-3	Day 4	Week 2	Week 3	Week 4	Week 11	Week 12 (±3 days)
Written informed consent	X							
Demographic data (incl. height and weight)	X							X ^a
Kinesia-ONE subject assessments (measured in triplicate)	X ^b							X
UPDRS	X							X
Patient engagement questionnaire	X							X
PDQ-39	X							X
Verification of inclusion/exclusion criteria	X							
Randomization	X							
C Group: Start treatment with Neupro 2mg or 4mg preferably on Day 1 but no later than Day 4 (dose adjustments during study are performed per standard of care)		X						X
C Group: Record Neupro dose		X						X
E Group: Kinesia-360 device training and distribution of equipment	X							
E Group: Subject wears Kinesia-360 wrist and ankle devices on Days 2 and 3 at home for baseline			X					
E Group: Start treatment with Neupro 2mg or 4mg on				X				

Day 4								
E Group: Record Neupro dose ^c			X					X
E Group: Reminder phone calls from site to subject at beginning of Weeks 2, 3, 4 and 11 (remind subject to charge devices and wear devices on at least 2 consecutive days during Weeks 2, 3, 4 and 11)				X ^d	X ^d	X ^d	X ^d	
E Group: Subject wears Kinesia-360 wrist and ankle devices on at least 2 consecutive days at home				X	X	X	X	
E Group: Subject and Investigator access Kinesia-360 device reports (subjects via device app, Investigators via GLNT web portal)					X			X
E Group: Investigator combines standard of care with Kinesia-360 motor symptom reports to adjust Neupro dose and is encouraged to contact the subject by phone to discuss motor symptom reports and potential Neupro dose adjustments anytime between V1 and V2 based on clinical judgment					X			
E Group: Subject returns Kinesia-360 device equipment to site								X
Record adverse events	X							X
Record concomitant medications	X							X

APP=application; C Group=Control Group; E Group=Experimental Group; EOS=End of Study; EW=Early Withdrawal; GLNT=Great Lakes Neuro Technologies, Inc.; PDQ-39=39-Item Parkinson's disease questionnaire; UPDRS=Unified Parkinson's Disease Rating Scale; V=visit

^a Only weight at V2.

^b The average of the triplicate resting tremor scores and triplicate finger tapping scores from Kinesia-ONE must be >1.0 to be eligible for inclusion in this study.

^c Subjects in the Experimental Group will be prompted to record Neupro dose in device app during each use of Kinesia-360 between V1 and V2.

^d Subjects in the Experimental Group are to use Kinesia-ONE on at least 2 consecutive days during Weeks 2, 3, 4 and 11, but are free to use the device as often as they like between these time points prior to Visit 2.

5.3 Rationale for study design and selection of dose

The Neupro dosing regimen used in PD0049 follows standard of care, and is in line with the approved dosing regimen for rotigotine in the treatment of Parkinson's disease (ie, up to 8mg/24h, depending on the stage of the disease).

As described in [Section 2](#), the focus of this study is on optimizing the benefits of Neupro in patients with Parkinson's disease by using wearable devices to help the Investigator optimize the evaluation of motor symptoms and improve customized dosing.

To that end, PD0049 employs Kinesia wearable technologies that allow for accurate, consistent, and ongoing measurement of motor activity under ambulatory conditions to provide the Investigator with additional information to further enhance his/her ability to evaluate subjects' motor symptoms more accurately and, via providing the patient with the optimal Neupro dosing regimen, ensure better patient outcomes in a more timely manner. Both Kinesia devices will be used in accordance with their labelled instructions.

6 SELECTION AND WITHDRAWAL OF SUBJECTS

6.1 Inclusion criteria

To be eligible to participate in this study, all of the following criteria must be met:

1. Subject is newly prescribed Neupro and is expected to commence Neupro treatment. Historical Neupro treatment is permitted.
2. An Institutional Review Board (IRB) approved written Informed Consent form (ICF) is signed and dated by the subject, before any study-related procedures.
3. Subject is considered reliable and capable of adhering to the protocol, visit schedule, completion of the diary, and using Kinesia devices according to the judgment of the Investigator.
4. Male or female subject, ≥ 18 years of age at the time of the Screening Visit.
5. Subject has Parkinson's disease, defined by the cardinal sign, bradykinesia, plus the presence of at least 1 of the following: tremor at rest, rigidity or impairment of postural reflexes, and without any other known or suspected cause of Secondary Parkinsonism.
6. Subject experiences motor symptoms associated with Parkinson's disease that are not sufficiently controlled by current therapy. The average of the triplicate resting tremor scores and triplicate finger tapping scores from Kinesia-ONE (6 scores in total) must be >1.0 .

6.2 Exclusion criteria

Subjects are not permitted to enroll in the study if any of the following criteria is met:

1. Subject is currently participating in any study with an investigational medicinal product (IMP) or investigational device.
2. Subject has any medical, neurological or psychiatric condition (eg, previous stroke, bipolar disorder, dementia, hallucinations, psychosis or severe depression, and drug or alcohol abuse) which, in the opinion of the Investigator, could jeopardize or would compromise the subject's ability to participate in this study.

3. Subject with Deep Brain Stimulation (DBS) device implant.

6.3 Withdrawal criteria

Subjects are free to withdraw from the study at any time, without prejudice to their continued care.

Subjects should be withdrawn from the study if any of the following events occur:

1. Subject develops an illness that would interfere with his/her continued participation.
2. Subject is noncompliant with the study procedures in the opinion of the Investigator.
3. Subject withdraws his/her consent.
4. The sponsor or a regulatory agency requests withdrawal of the subject.

For assessments to be performed in case of an Early Withdrawal, refer to [Table 5-1](#).

Investigators should attempt to obtain information on subjects in the case of withdrawal or discontinuation. For subjects considered as lost to follow up, the Investigator should make an effort (at least 1 phone call and 1 written message to the subject), and document his/her effort (date and summary of the phone call and copy of the written message in the source documents) to complete the final evaluation. All results of these evaluations and observations, together with a narrative description of the reason(s) for discontinuing the subject, including the date of discontinuation, must be recorded in the source documents. The electronic Case Report form (eCRF) must document the primary reason for withdrawal or discontinuation.

Investigators should contact the Medical Monitor, whenever possible, to discuss the withdrawal of a subject in advance.

For handling of dropouts, refer to [Section 12.6](#).

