8.1 Visit 1 /Screening

The Screening examinations will be completed within 4 days, the first of which will take place at the study site (in clinic) and will include the following:

Day 1, in clinic:

- Sign ICF
- Control Group and Experimental Group: Subject wears Kinesia-ONE sensor on the most affected side in the clinic to measure specific motor tasks in triplicate. Calculation of the average of triplicate resting tremor scores and triplicate finger-tapping speed scores (ie, 6 scores in total) must be >1.0 for subject inclusion in the study.
- Verification of inclusion/exclusion criteria and collection of demographic data (including weight and height)
- PDQ-39
- Investigator performs UPDRS assessment
- Patient Engagement Questionnaire
- Randomization (Control Group [without Kinesia-360 device use at home]/Experimental Group [with Kinesia-360 device use at home])
- Experimental Group: Trained in-clinic on Kinesia-360 device (and sent home with the device)
- Control Group: Start treatment with Neupro as prescribed (preferably on Day 1, but no later than Day 4); record date and dose
- Control Group and Experimental Group: Recording of AEs and concomitant medications

8.2 Week 1

Day 2 and 3, home:

- Experimental Group: Subject wears Kinesia-360 wrist and ankle devices on Days 2 and 3 at home for baseline
- Experimental Group: Recording of concomitant medications and Neupro dose via APP

Day 4, home:

- Experimental Group: Start treatment with Neupro as prescribed; record date and dose via APP

- Experimental Group: Recording of concomitant medications

8.3 Weeks 2, 3, and 4

Control Group, home:

- Investigator uses standard of care to adjust Neupro dose as needed.
- Phone contact initiated by subject or Investigator as needed. Documentation of any contact or dosage adjustment.

Experimental Group, home:

- Subject uses Kinesia-360 at least on 2 consecutive days at home weekly to measure motor symptoms.
- Subject accesses Kinesia-360 motor symptom reports on device following each day of measurements.
- Investigator receives Kinesia-360 motor symptom reports via web portal following each day of measurements.
- Investigator combines standard of care with weekly Kinesia-360 motor symptom reports to adjust Neupro dose as needed.
- Phone contact initiated by subject or Investigator as needed and dispatch of Kinesia-360 motor symptom reports. Documentation of any contact or dosage adjustment.
- Recording of concomitant medications and Neupro dose via APP.

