- A reminder phone call from the site to the subject each week during Weeks 2, 3, and 4 to ensure the subject will perform the protocol-requested Kinesia-360 assessments on 2 consecutive days per week. In addition, the subject should be reminded to charge the device and phone batteries the night prior to assessments.

8.4 Week 5 up to Week 12

Control Group, home:

- Treatment of subjects as per standard of care.
- Phone contact initiated by subject or Investigator as needed. Documentation of any contact or dosage adjustment.

Experimental Group, home:

- A reminder phone call from the site to the subject during the week prior to Visit 2 to ensure the subject will perform the protocol-requested Kinesia-360 assessments on 2 consecutive days. In addition, the subject should be reminded to charge the device and phone batteries the night prior to assessments.
- Optional: Subject may use Kinesia-360 as desired between Week 5 and Visit 2 (Week 12).
- Subject receives Kinesia-360 motor symptom reports on device following each day of measurements.

- Investigator receives Kinesia-360 motor symptom reports via web portal and by email following each day of measurements.
- Treatment of patients as per standard of care and dispatch of any Kinesia-360 motor symptom report.
- Phone contact initiated by subject or Investigator as needed and dispatch of Kinesia-360 motor symptom reports. Documentation of any contact or dosage adjustment.

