These daily scores will be used to derive the scores per visit week. The daily scores will be averaged from 2 consecutive days of wearing in the respective assessment week. Assessments on study day 8 to 14 are eligible for Week 2 scores, assessments on study day 15 to 21 are eligible for Week 3 scores, assessments on study day 22 to 28 are eligible for Week 4 scores, assessments on study day 43 to 56 are eligible for Week 7/8 scores, and assessments on study day 71 to 77 are eligible for Week 11 assessments. The Week 7/8 is an artificially added Week, which considers the data collected on voluntary basis during that time interval, and therefore might have sparse data. If more than 2 consecutive assessments are available for Week 7/8, the latest 2 consecutive values will be considered. The same applies for the assessments in Week 2, Week 3, Week 4, and Week 11: If more than 2 consecutive assessments are available per week, the latest 2 consecutive values will be considered.

In addition, the maximum relative day of Kinesia-360 usage will be listed, and the number of days the subject used the Kinesia-360 device will be calculated by subject and summarized.

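### The noncompliance rule in Protocol 6.3 can end Week 12 follow-up for low device wear, a recurring duty that only the Experimental Group has

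*Protocol*

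**What the plan says.** **The rule.** Protocol 6.3 opens with "Subjects should be withdrawn from the study if any of the following events occur", and criterion 2 reads "Subject is noncompliant with the study procedures in the opinion of the Investigator". It gives no definition of noncompliance, no wear threshold and no exemption for the device. Investigators are asked to discuss a withdrawal with the Medical Monitor beforehand where possible.

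**Experimental Group between visits.** Protocol 8.2: "Experimental Group: Subject wears Kinesia-360 wrist and ankle devices on Days 2 and 3 at home for baseline". Protocol 8.3, for Weeks 2 to 4: "Subject uses Kinesia-360 at least on 2 consecutive days at home weekly to measure motor symptoms". Table 5-1 adds Week 11. Subjects also enter Neupro dose and other medications in the app. Sites make reminder calls to "ensure the subject will perform the protocol-requested Kinesia-360 assessments on 2 consecutive days per week", and Investigators receive a report after each day of measurement.

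**Control Group between visits.** There is no home device, no scheduled call and no home recording. Protocol 8.3 and 8.4 provide for standard of care and contact as needed. The one timed item that can fall at home is starting Neupro by Day 4.

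**After withdrawal.** Protocol 8.6 repeats the Visit 2 assessments at an Early Withdrawal Visit, and SAP 3.2.3 and 4.2 analyse those data as Visit 2. Otherwise efficacy uses observed cases of the FAS (Protocol 12.3.1), in general without imputation (Protocol 12.6). Neupro is prescribed independently of the study, and "Neupro will not be supplied by UCB" (Protocol 5.1).

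**Device use as a variable.** SAP 8.2.1 already states that "the number of days the subject used the Kinesia-360 device will be calculated by subject and summarized".

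**The concern.** The trial compares two ways of titrating Neupro: standard care, and standard care plus feedback from Kinesia-360. How much subjects wear the device is part of the second strategy, so a subject who wears it little is still informative about that strategy. Criterion 2 lets that behaviour end study participation, and the Control Group has no recurring counterpart. Detection is also one-sided, since reminder calls and device reports reveal non-wear, while SAP 7 says that neither diary nor drug accountability data are collected.

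Three consequences follow for subjects withdrawn in this way:

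- **(a)** Those who do not attend an Early Withdrawal Visit contribute no UPDRS III or Kinesia-ONE change.
- **(b)** Those who do attend contribute a value taken before Week 12. Three of the four post-baseline wear weeks are Weeks 2, 3 and 4. Protocol 2 says that most patients reach an effective dose within 3 or 4 weeks in early disease and 3 to 7 weeks in advanced disease. UPDRS III, Neupro dose and the number of dose changes may then be recorded mid-titration.
- **(c)** Study withdrawal is not drug discontinuation, but Neupro status is unobserved from then on. Continuation is a primary objective, and the logistic regression in SAP 8.1.2 has no rule for these subjects.

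**Working it through.** The plan has no figure to reproduce: Protocol 12.8 gives no effect size, SD, power or dropout rate. For orientation, 20 per arm at two-sided 0.05 gives 80% power for a difference of about 0.89 SD and 35% at 0.5 SD.

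**Inputs.** 20 subjects per arm (Protocol 5.1.2); two-sided 0.05, exploratory (Protocol 12.2). Assumed, because the documents are silent: k = 2 or 4 Experimental subjects withdrawn for low wear; their outcome g = 0.25 to 1.0 SD worse than the other Experimental subjects; a share e of them supplying Early Withdrawal data. Outcome SD = 1 and no true group difference.

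**(a) Selection.** Let w = k/20 and set the mean of all 20 to 0. The good wearers then average w·g and the low wearers w·g − g. With e = 0, only the good wearers remain:

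- bias = w·g, in favour of the Experimental Group
- SE = √(1/(20 − k) + 1/20)

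| k | bias, g = 0.25 | bias, g = 1.0 | SE | Rejection rate under the null, g = 1.0 |
|---|---|---|---|---|
| 2 | 0.10 × 0.25 = 0.025 SD | 0.10 × 1.0 = 0.10 SD | 0.325 | 0.061 |
| 4 | 0.20 × 0.25 = 0.05 SD | 0.20 × 1.0 = 0.20 SD | 0.335 | 0.092 |

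If half supply Early Withdrawal data (e = 0.5), the bias is 0.012 to 0.089 SD. For k = 4 and g = 1.0: (16 × 0.2 + 2 × (0.2 − 1))/18 = 1.6/18 = 0.089. The rejection rate is then at most 0.059. If all supply it (e = 1), the bias is 0 and the rate 0.050. This model ignores timing.

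**(b) Early values.** Suppose the withdrawn subjects attend the visit but lack s points of the UPDRS III improvement they would have had by Week 12. The Experimental mean improvement falls by w·s. With an assumed s = 3, that is 0.10 × 3 = 0.3 points (k = 2) or 0.20 × 3 = 0.6 points (k = 4). This acts against the Experimental Group, opposite in sign to (a), so the net direction depends on how many attend.

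**(c) Neupro continuation.** Each subject is 1/20 = 5 percentage points of the arm's rate, so 2 withdrawn leave 10 points unknown and 4 leave 20. As an illustration, assume a true discontinuation rate of 25% in each arm (5 of 20), with 4 Experimental subjects withdrawn, 2 of whom stop Neupro unseen. The observed Experimental rate is (5 − 2)/20 = 15% if the withdrawn count as continuing, or (5 − 2)/16 = 18.8% if they are dropped, against 25% in the Control Group.

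**The case against.** Criterion 2 rests on the Investigator's opinion, does not mention the device, and invites a prior conversation with the Medical Monitor. The protocol's stated response to possible non-wear is a reminder call, and inclusion criterion 3 selects subjects judged able to use the devices. Withdrawn subjects who attend the Early Withdrawal Visit have the full Visit 2 battery and remain in the FAS. Controls go 12 weeks without scheduled contact, whereas Experimental subjects have calls and app capture of Neupro discontinuation (Protocol 10.3.1), so their status up to withdrawal may be better observed. The sizes rest on assumed inputs, and no p-value is read as significance.

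Most of this stands, and it rules out several stronger readings that a reader might infer:

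- **Low wearers are removed automatically.** The text directs withdrawal only once the Investigator judges noncompliance.
- **A control subject cannot meet the criterion.** One can, by starting Neupro late or missing Visit 2. What the Control Group lacks is a recurring home procedure to fail.
- **Withdrawn subjects vanish from the analysis.** That is so only without an Early Withdrawal Visit.
- **Non-wear also empties the per-protocol set.** SAP 3.4 leaves the deviation criteria to another document, and nothing shows that non-wear is one of them.

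The objection does not remove the asymmetry in what can trigger withdrawal. Nor does the Early Withdrawal Visit cure the early timing of the values or recover later Neupro status.

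**Conclusion.** The point holds as a design weakness with a cheap remedy. A criterion worded for both arms permits and directs withdrawal for low device wear in one of them, and that wear belongs to the strategy under test. On the assumptions shown, the selection bias is about 0.025 to 0.20 SD in favour of the Experimental Group when 2 to 4 of 20 leave without final data. It shrinks towards zero as more attend the Early Withdrawal Visit. Early values pull the other way if improvement was still to come. The discontinuation rate loses 5 percentage points of information per withdrawn subject.

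A reader might conclude that the randomised comparison is undermined for every primary objective. The documents do not support that: the number of such withdrawals is unknown, the two effects on motor scores have opposite signs, and all tests are exploratory. The effect is on how the group differences are interpreted, above all for continuation on Neupro.

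**What to change.** Amend Protocol 6.3 criterion 2 to say that failing to wear, charge or record with Kinesia-360 is not by itself a reason to withdraw a subject from the study. Such subjects stay in follow-up to Visit 2 for all two-group assessments, including Neupro status and dose. Non-wear is reported through the days-of-use variable already in SAP 8.2.1. The change concerns study follow-up only and leaves treatment decisions untouched. No per-protocol rule is proposed: that set is a sensitivity set meant for subjects who followed the plan more closely, and excluding non-wearers from it is a defensible choice.

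If follow-up is already complete, show withdrawals for noncompliance by arm. Protocol 6.3 requires the primary reason in the eCRF, and SAP 5.1 already plans a table of reasons.

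The cost is a short protocol amendment. The downside is that low wearers who stay will slightly dilute the contrast, which is also how the strategy would perform in practice.
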